Subjects will stop DB treatment and will be discharged from the clinical site or designated confinement location, after the first blue dyed stool following the second dye administration is collected (Visit 5). This could occur at hospitalization/confinement Day 6, 7 or 8, depending on each subject's gastrointestinal motility.

Subjects who withdraw during any Part of the study will immediately enter the Post-Treatment Follow-Up Period, and will undergo early discontinuation activities as specified in Appendix C, Visit 5.

After completing the Part to which the subject was originally enrolled, the subjects may be given the opportunity to participate in the other Study Part. If the subject agrees to participate in the other study Part, he/she will re-start his/her usual diet and will be given a

supply of open label Creon[®], at the dose they received during the screening period, to be taken during this period of up to 30 days, while eligibility for the other Part is re-assessed. The subject will then return to the clinical site or designated confinement location for randomization into the other Study Part. If visit 1 of the next Part does not occur within 30 days of the last dose of study drug (Visit 5) of the previous part, the subject will not receive any additional open label Creon[®] (Pancrelipase) 24,000 USP units (lipase) past the amount provided for the first 30 days, and the subject will need to be reconsented/rescreened for the next study part.

Post-Treatment Follow-Up Period (Visit 5 to Visit 6)

During the follow-up period for both study parts, subjects will be given at Visit 5 a supply of open label Creon[®] at the dose they received during the screening period to be taken during this period, along with their usual diet.

A safety follow-up telephone contact (Visit 6) will be performed 30 days after discharge upon completion of DB Treatment Period 2 (or following study withdrawal) to verify the subject's well-being and to assess for AEs and changes in concomitant medication use. If a subject is participating in both study Parts and they are starting the second study Part \leq 30 days following completion of DB Treatment Period 2 of the previous Part, Visit 6 can be completed on the same day as the start of the next study Part.

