Duration of exposure to OL Creon between DB Treatment Period 1 (TP1) and DB Treatment Period 2 (TP2) and after TP2 will be summarized for the Safety Analysis Set for study Part 1 and Part 2 using SA-P1 or SA-P2, respectively. Duration of treatment is defined for each subject as last dose date of OL Creon prior to Visit 4 minus first dose date of OL Creon after Visit 3 + 1 plus last dose date of OL Creon after Visit 5 minus first dose date of OL Creon after Visit 5 + 1. In other words, the total duration for the interval between TP1 and TP2, and the period after TP2 will be summed to calculate the duration of open-label treatment following randomization. Duration of treatment will be summarized using the number of subjects treated, mean, standard deviation, median, minimum and maximum.

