9.2.2 AEs During the Open Label Period(s)

AEs and SAEs that have a start date during an Open Label Period will be summarized by SOC and PT for the Open Label Safety Analysis Set for study Part 1 and Part 2 using OLSA-P1 and OLSA-P2, respectively. These AEs and SAEs include the following:

- For Part 2 and for Part 1 subjects enrolled under protocol amendment 6 or later:
 AEs and SAEs that have a start date either on or after the first dose date of OL
 Creon in Screening Period, and before the first dose of the study drug in DB
 Treatment Period 1 (if the subject entered the DB treatment period), or on or
 after the first dose date of OL Creon in the Screening Period (if the subjects
 never entered the DB treatment period)
- For Part 1 subjects enrolled under protocol amendment 5 or earlier: AEs and SAEs that have a start date either on or after the first dose date of the Maintenance Period, and before the first dose of the study drug in DB Treatment Period 1 (if the subject entered the DB treatment period), or on or after the first dose date of the Maintenance Period (if the subject never entered the DB treatment period)
- For Part 1 and Part 2: AEs and SAEs that have a start date either on or after the first dose date of the Open Label Period after DB Treatment Period 1, and before the first dose of the study drug in DB Treatment Period 2 (if the subject entered DB Treatment Period 2), or on or after first dose date of the Open Label Period after DB Treatment Period 1 (if the subject never entered the DB treatment period)
- For Part 2 and for Part 1 subjects enrolled after protocol amendment 6: AEs and SAEs that have a start date either on or after the first dose date of OL Creon in the Follow Up Period after DB Treatment Period 2

Listing of SAEs during the Open Label Period(s) will also be provided for the Open Label Safety Analysis Set.

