9.2.3.1 Treatment-Emergent Adverse Events

Treatment-emergent AEs for the regimen administered in DB Treatment Period 1 are defined as reported AEs that have a start date either on or after the first dose of the study drug during DB Treatment Period 1, and up to the end of DB Treatment Period 1, defined as the earliest of: the first dose date of OL Creon after Visit 3, the start of the first dose of DB Treatment Period 2, or 30 days after the last dose of study drug during DB Treatment Period 1. For the regimen administered in DB Treatment Period 2, treatment emergent AEs are defined as reported AEs that have a start date either on or after the first dose of study drug during DB Treatment Period 2, and up to the end of DB Treatment Period 2, defined as the earlier of the first dose date of OL Creon after Visit 5 or 30 days after the last dose of study drug during DB Treatment Period 2.

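### SAP 9.2.2 admits Part 1 follow-up adverse events by enrolment version rather than by receipt of open-label Creon, so an excluded subject who took it after Visit 5 has later non-serious events in no listed table

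*SAP*

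**What the plan says.** SAP 9.2.2 opens with a general rule, "AEs and SAEs that have a start date during an Open Label Period will be summarized by SOC and PT", applied to everyone in the open-label safety set. It then lists four windows that this includes:

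- Bullet 1 (screening): "For Part 2 and for Part 1 subjects enrolled under protocol amendment 6 or later".
- Bullet 2 (maintenance): Part 1 subjects enrolled under Amendment 5 or earlier.
- Bullet 3 (between periods): both Parts, with onset bounds written as "first dose date of the Open Label Period after DB Treatment Period 1, and before the first dose of the study drug in DB Treatment", that is, up to the start of Period 2 dosing. It has no amendment condition.
- Bullet 4 (follow-up after Period 2): "For Part 2 and for Part 1 subjects enrolled after protocol amendment 6".

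Other sections bear on the same follow-up days:

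- SAP 9.2.3.1 closes the Period 2 treatment-emergent window at a point "defined as the earlier of the first dose date of OL Creon after Visit 5 or 30 days after the last dose" of double-blind drug. It has no amendment condition.
- SAP 6.0 adds "last dose date of OL Creon after Visit 5 minus first dose date of OL Creon after Visit 5" (plus one day) to post-randomization open-label exposure, for the whole Safety Analysis Set of each Part.
- SAP 4.0 puts in the Open Label Safety Analysis Set anyone with at least one open-label dose in any study period.
- Protocol 8.1.3 asks for events on open-label Creon to be summarized separately for screening and for the time after randomization, with no version test.
- Protocol 5.1 now states: "During the follow-up period for both study parts, subjects will be given at Visit 5 a supply of open label Creon".

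**The concern.** The two windows have to meet. When the treatment-emergent window closes because open-label Creon has started, the open-label window should open for the same subject on the same date. Here the closing rule depends on what the subject took, and the opening rule depends on the protocol version at enrolment. Where the two disagree, the subject leaves the blinded table and enters no listed open-label window, although SAP 6.0 still counts the exposure.

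Enrolment version is also a poor proxy for what was dispensed at Visit 5. The interval between periods can last 28 days and may be extended in exceptional circumstances (Protocol 5.1), so a subject can enrol under one amendment and reach Visit 5 under the next. In addition, bullets 1 and 4 word the cut differently, and two programmers could code them differently. At stake is the completeness of the descriptive open-label adverse event tables in a Part of about 26 randomized subjects.

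**Working it through.** The plan states no figure to reproduce, so the check applies the two windows as written.

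**Set-up.** Let *d* = 1 to 30 be the day of onset after the last double-blind dose in Period 2, and *s* the day of the first open-label dose after Visit 5.

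- Treatment-emergent (SAP 9.2.3.1): covered if *d* ≤ min(*s*, 30), or *d* ≤ 30 if there was no open-label dose.
- Open-label follow-up (SAP 9.2.2, bullet 4): covered if *d* ≥ *s* and the enrolment condition is met.
- Days uncovered for a subject who fails the condition: 30 − min(*s*, 30). With *s* = 1 this is 30 − 1 = 29. With no open-label dose it is 30 − 30 = 0.

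**Follow-up days (of 30) in neither window**

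| Enrolled under | Open-label Creon after Visit 5 | *after* = Amendment 6 onward | *after* = strictly later version |
|---|---|---|---|
| Amendment 5 or earlier | none | 0 | 0 |
| Amendment 5 or earlier | from day 1 | 29 | 29 |
| Amendment 6 | none | 0 | 0 |
| Amendment 6 | from day 1 | 0 | 29 |
| Amendment 7 | none, or from day 1 | 0 | 0 |

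**How many subjects.** SAP 2.4 gives 10 subjects enrolled at the time of Amendment 6; Part 1 plans about 26 randomized.

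- *Amendment 6 onward*: at most 10, or 10/26 = 38%, and 10 × 29 = 290 subject-days. This assumes that all 10 were in Part 1 and randomized, that all started open-label Creon on day 1 of follow-up, and that nobody else enrolled under an older version after that count. The actual number is those among them who took open-label Creon after Visit 5. The documents do not give it, and it may be 0.
- *Strictly later version*: subjects enrolled under Amendment 6 would be lost as well. The Part 1 re-estimation, planned at 13 subjects (SAP 2.4.1), was complete by Amendment 7, so about 13 − 10 = 3 is a rough lower figure. The upper figure is 26 − 10 = 16, if nobody in Part 1 enrolled under Amendment 7.

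**After the change.** If bullet 4 applied to every subject with an open-label dose after Visit 5, every row of the table would be 0: takers are covered from the first dose and non-takers to day 30.

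**The case against.** Four points can be made for the plan.

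1. *The 30-day limit already covers earlier enrolees.* A reader might infer that follow-up events of all Part 1 subjects outside bullet 4 are lost. The documents do not support that, because SAP 9.2.3.1 keeps anyone without follow-up open-label Creon in the treatment-emergent window for 30 days. Bullet 4 may be restricted precisely because earlier enrolees received none. That is a fair inference, but the documents do not confirm it: the Amendment 7 summary says only that text was added to clarify that open-label drug is given in follow-up. The point stands for non-takers and leaves takers exposed.

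2. *The word after means Amendment 6 onward.* This is probably right. SAP 6.0 uses screening before and after Amendment 6 as complements, and bullets 1 and 2 split at Amendment 6. The version history dates the open-label summaries to version 3.0 (05 Apr 2021), before the Amendment 7 synopsis (15 September 2021), and lists no later change to 9.2.2. A loss of 3 to 16 subjects therefore belongs to the strict reading only and should not be taken as the expected size.

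3. *The lead sentence covers everything.* The general rule of 9.2.2 has no restriction and the bullets are introduced as inclusions. If that governs, bullet 4's condition does nothing and contradicts the rule above it, so it still needs correcting.

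4. *Serious events are caught elsewhere.* A reader might infer that serious events drop out too. That is not shown. The 9.2.2 listing covers serious events in the open-label periods without a version test. SAP 9.2.3.4 does not limit its serious-event summary to treatment-emergent events, although it sits under the double-blind heading. SAP 9.2.3.2 counts all deaths. Non-serious events have only the lead sentence to fall back on.

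Nor can one say that reported rates would be too low for the exposure shown: the SAP plans subject percentages, not exposure-adjusted rates, and reports the exposure and the open-label events on different analysis sets.

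**Conclusion.** The mismatch holds in a limited form. The listed windows leave a gap only for a Part 1 subject who fails bullet 4's enrolment condition and took open-label Creon after Visit 5, and only for events after that first dose. Non-serious events are the ones clearly without a listed home. This also departs from Protocol 8.1.3, which sets no version test. The size rests on the reading of *after* and on how many earlier enrolees were dispensed follow-up Creon, which the sponsor can establish from dosing records. The point is minor and confined to descriptive safety output. It does not touch the CFA comparison, the sample size or the type I error.

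**What to change.** Replace the condition in SAP 9.2.2 bullet 4 with actual receipt, for example: *For any subject in Part 1 or Part 2 who took OL Creon after Visit 5: AEs and SAEs with a start date on or after the first such dose.* This matches SAP 6.0 and 9.2.3.1 and removes the ambiguity in *after*. It would also help to state whether anyone enrolled under Amendment 5 or earlier received open-label Creon in follow-up.

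The cost is one SAP sentence. The dosing dates are already needed for 6.0 and 9.2.3.1, so no new data are required, and the change does no harm if the affected number proves to be 0.

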9.2.3 AEs During the Double-Blind Treatment Period

[figure not shown]
9.2.3.1 Treatment-Emergent Adverse Events

Treatment-emergent AEs for the regimen administered in DB Treatment Period 1 are defined as reported AEs that have a start date either on or after the first dose of the study drug during DB Treatment Period 1, and up to the end of DB Treatment Period 1, defined as the earliest of: the first dose date of OL Creon after Visit 3, the start of the first dose of DB Treatment Period 2, or 30 days after the last dose of study drug during DB Treatment Period 1. For the regimen administered in DB Treatment Period 2, treatment emergent AEs are defined as reported AEs that have a start date either on or after the first dose of study drug during DB Treatment Period 2, and up to the end of DB Treatment Period 2, defined as the earlier of the first dose date of OL Creon after Visit 5 or 30 days after the last dose of study drug during DB Treatment Period 2.

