- *If the subject had symptomatic infection:* At least 2 consecutive negative COVID-19 tests, ≥ 24 hours apart after at least 7 days have passed since recovery, defined as resolution of fever without use of antipyretics **and** improvement in respiratory symptoms (e.g., cough, shortness of breath).
- *If the subject had asymptomatic infection:* At least two negative COVID-19 tests in a row, ≥ 24 hours apart after at least 7 days have passed since prior positive test result.

Please see Section 5.3.1.1 for directions on retesting/rescreening after a positive COVID-19 test.

Re-screened subjects will sign a new ICF and all Screening Visit procedures (except FE-1) have to be repeated.

Double-Blind Treatment Period for Study Part 1 and/or Study Part 2

Once study eligibility has been confirmed, subjects will be enrolled into the DB Treatment Period of either Part 1 or Part 2. After they complete the Part they were initially enrolled in, the subject may elect to participate in the other Part.

DB Treatment Period 1 (Visit 2 to Visit 3)

Eligible subjects will be admitted to the clinical site or designated confinement location, in the morning (prior to breakfast) of Visit 2 or in the evening (after dinner) on the previous day and will be hospitalized/confined at the clinical site or designated confinement location for approximately 6 to 8 days, depending on each subject's gastrointestinal motility.

At Visit 2 (DB Treatment Period 1 Day 1), subjects will be allocated into Study Part 1 or Part 2 and randomized in a 1:1 ratio to 1 of the 2 treatment sequence arms within their study Part, as shown below:

Part 1:

Sequence Arm	Treatment Period 1	Treatment Period 2
А	Pancrelipase DR capsules MP	Creon [®] (Pancrelipase) DR
В	Creon [®] (Pancrelipase) DR capsules	Pancrelipase DR capsules MP

DR = Delayed release; MP = Modernized Process uniform coated pellets, large scale

Part 2:

Sequence Arm	Treatment Period 1	Treatment Period 2
С	Pancrelipase DR capsules AAPIS	Creon [®] (Pancrelipase) DR capsules
D	Creon [®] (Pancrelipase) DR capsules	Pancrelipase DR capsules AAPIS

AAPIS = Delayed-release capsules of pancrelipase manufactured at an Alternate Active Pharmaceutical Ingredient Site; DR = Delayed release

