Subject will stop DB treatment and will be discharged from the clinical site or designated confinement location, (or begin preparation for DB Treatment Period 2) after the first blue dyed stool following the second dye administration is collected (Visit 3). This could be hospitalization/confinement Day 6, 7 or 8, depending on each subject's gastrointestinal motility.

If subject chooses to leave the clinical site or designated confinement location after DB Treatment Period 1, subject will re-start his/her usual diet and will be given a supply of open label Creon[®] at the dose of open label Creon[®] they received for the screening period to be taken during this period, until returning to the clinical site or designated confinement location, for DB Treatment Period 2. The interval between DB Treatment Period 1 and DB Treatment Period 2 will last up to a maximum of 28 days: In exceptional

circumstances, such as impact by COVID-19-related activities, this period may be extended upon specific consultation with the sponsor. If the subject elects to continue directly into DB Treatment Period 2, and site capacity allows, Visit 4 will be the day following Visit 3.

DB Treatment Period 2 (Visit 4 to Visit 5)

Subject will again be hospitalized/confined (or continue to be hospitalized/confined) at the clinical site or designated confinement location, for approximately 6 to 8 days, starting in the morning (prior to breakfast) of Visit 4 or in the evening (after dinner) on the previous day.

Before any study drug administration on DB Treatment Period 2 Day 1 (Visit 4), subject's weight will be confirmed to be 40 kg or more. Then subjects will stop current open label Creon[®] (if receiving it) and will receive DB study drug and an individualized diet with 100 grams daily fat content, a minimum of 1 g/kg of daily protein and normal to low fiber content for 6 - 8 days. Each subject's diet for the two treatment periods will be created at the same time by a site-based dietitian using ABVDiet, after an interview with the subject, and reviewed and approved by a central dietitian, prior to Visit 2. Dietary surveillance and stool collection will be performed as during DB Treatment Period 1.

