5.3.1.1 Study Procedures

Informed Consent

At the Screening Visit, signed informed consent (and subject's assent as applicable) will be obtained from the subject before beginning any study-specific procedure. A prescreening consent may also be obtained from the subject prior to the screening visit so a stool sample can be collected and brought to the study site at the Screening Visit. Details on how informed consent/assent will be obtained and documented are provided in Section 9.3.

Subjects who have signed informed consent/assent and do not complete the study-specific procedures during the Screening Period will be considered screen failures. The reason(s) for screen failure will be documented in the source documents and will be captured in the eCRF.
Medical History

A complete medical history, including documentation of any clinically significant medical conditions and medications (including history of tobacco, nicotine-containing products and alcohol use) will be collected during the Screening Visit of the first part the subject is participating in. The Medical History form of the eCRF must contain all diseases/conditions for which the subject is taking concomitant medications.

For subjects who are participating in more than 1 study Part, the medical history will be reviewed at the screening visit for the next part the subject is participating in and updated for any new information available.

Pancreatic Enzyme Replacement Therapy (PERT)

Under the direction of their usual treating physician, at the screening visit subjects will start receiving open label Creon[®] at their usual established dose until all eligibility criteria are confirmed and the subject randomized, or until the subject is screen-failed.

For subjects who enter DB Treatment Period 2 directly from DB Treatment Period 1 (without leaving the hospital/confinement site): during the 24 h period until Treatment Period 2 can be started, subjects will be maintained at their usual diet and will be administered open label Creon[®] at the dose they received during the screening period. This daily dose of open label Creon[®] should be recorded in the eCRF.

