8.1.3 Safety Analysis

Safety analyses will be carried out using the Safety Analysis Set. Treatment-emergent AEs and SAEs, will be summarized and reported. Treatment-emergent AEs for DB Treatment Period 1 are defined as reported AEs that have a start date either on or after the first dose of the study drug during DB Treatment Period 1 and up to the end of DB Treatment Period 1. For DB Treatment Period 2, treatment emergent AEs are defined as reported AEs that have a start date either on or after the first dose of study drug during DB Treatment Period 2 and up to the end of DB Treatment Period 2. Adverse Events that occur during the administration of OL Creon[®] will be summarized separately for events that happen during the screening period and after randomization. The number and percent of subjects experiencing AEs will be tabulated by system organ class (SOC) and Medical Dictionary for Drug Regulatory Activities (MedDRA®) preferred term. In addition, summary of AEs by severity and relationship to study drug will be presented. Serious AEs, or AEs that lead to premature study discontinuation will be listed and described in detail. All these summaries will be done by treatment group. Mean change in vital signs and laboratory variables at each visit will be summarized. The last evaluation prior to the first dose of DB study drug in the corresponding treatment period will be used as baseline for the analysis in that treatment period. A frequency table will be presented for Potentially Clinically Important (PCI) vital sign findings. Shift tables for laboratory variables will be presented according to the reference ranges (low, normal or high).

Due to the small number of subjects per treatment group, only summary statistics will be applied to all the safety parameters.

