2.4 Sample Size Determination

The sample size determination consists of a power calculation for the total number of evaluable subjects needed and assumptions for percentage of drop-outs for the total number of subjects enrolled. A non-inferiority margin of 12% is chosen for the study. This non-inferiority margin for comparing Pancrelipase DR MP to Creon® (Part 1) or comparing Pancrelipase DR AAPIS to Creon® (Part 2) was derived based on Creon's effect in a more comparable subject population in the historical study with a similar study design as follows:

Based on historical data from 4 placebo-controlled studies (Studies S223.3.101¹, S223.3.102², S245.3.126³, S245.3.127⁴), the effect in CFA is 36.8% (95% confidence interval: 32.6% – 41.0%) comparing Pancrelipase DR Capsules 24,000 with placebo.

Specifically, in the historical placebo-controlled Creon® Study S245.3.126³, which had a similar study design as Study M16-111 (as a two-period, two-sequence cross-over study conducted in an adult population at the same dose strength as M16-111), the effect of Creon® compared to placebo in CFA was estimated as 39.02% (95% CI: 32.3% – 45.8%) based on 31 enrolled CF subjects with confirmed EPI based on the eligibility criteria of a historical CFA < 70%, or current or historical Fecal Elastase-1 (FE-1) < 50 μ g/g. However, it is expected that the current Study M16-111 will enroll subjects with more severe EPI than the subjects in Study S245.3.126, as the enrollment criteria for EPI in the current study is more stringent: subjects need to have a baseline FE-1 less than 15 μ g/g to be enrolled. At the time of the protocol amendment 6, all subjects enrolled (N=10) in Study M16-111 had a screening FE-1 of less than 15 μ g/g and a screening CFA below 50%.

A subgroup analysis in Study S245.3.126 was performed to estimate the Creon effect in subjects with a more severe EPI, defined as having a CFA of 50% or less during the placebo treatment period (since the screening FE-1 value was not collected in Study S245.3.126). The Creon effect compared to placebo in CFA was estimated as 52.25% (95% CI: 47.0% - 57.5%) in this subject population. Based on the lower bound of the 95% CI for the estimate of Creon effect, a non-inferiority margin of 12% would preserve over 70% of that effect ((47-12)/47=74%).

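### The SAP's treatment-emergent AE window differs from the protocol's and depends on open-label Creon supply, so some Part 1 subjects may have unequal windows in their two periods

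*SAP*

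**What the plan says.** Protocol 8.1.3 counts Period 2 TEAEs as those starting "on or after the first dose of study drug during DB Treatment Period 2 and up to the end of DB Treatment Period 2", with the same rule for Period 1. The protocol's Definition of Terms ends the two periods at Visit 3 and Visit 5. There is no 30-day tail.

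SAP 9.2.3.1 keeps the idea of an end of period but redefines it. For Period 1 it is "defined as the earliest of: the first dose date of OL Creon after Visit 3, the start of the first dose of DB Treatment Period" (meaning the second period); a third limit falls 30 days after the last dose. For Period 2 it is "defined as the earlier of the first dose date of OL Creon after Visit 5 or 30 days after the last dose".

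Open-label Creon follows Period 1 on either route. Under Protocol 5.1, a subject who leaves the site goes home with a supply: "subject will re-start his/her usual diet and will be given a supply of open label Creon". Under Protocol 5.3.1.1, a subject who rolls over directly receives it "during the 24 h period until Treatment Period 2 can be started, subjects will be maintained at their usual diet".

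After Period 2 the documents are less uniform. The current protocol (5.1 and 5.5.1) supplies open-label Creon at Visit 5 in both Parts. The last bullet of SAP 9.2.2 restricts the follow-up open-label AE summary: "For Part 2 and for Part 1 subjects enrolled after protocol amendment 6". SAP 6.0 sums open-label exposure after Period 2 over the whole Safety Analysis Set, with no such restriction.

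SAP 9.1 presents the Safety Analysis Set by regimen. SAP 9.2.2 summarises open-label AEs by SOC and PT and mentions no split by preceding regimen.

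**The concern.** The percentage of subjects with TEAEs is the first safety endpoint in SAP 3.4, and showing it by regimen is the main safety comparison of each new product with Creon. In a crossover that comparison is easiest to read when a subject is observed for the same time on each product. Under the SAP rule, window length depends on whether open-label Creon was supplied afterwards, and that supply appears to have changed during Part 1. The same subject could then contribute about a week to one regimen and more than five weeks to the other.

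The two AE summaries also do not meet cleanly. The TEAE window closes on taking open-label Creon, whereas the follow-up open-label summary opens on the amendment in force at enrolment. A subject can satisfy the first condition and fail the second.

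**Working it through.** **Check of the time blocks.** The documents give no TEAE window length, but Protocol 5.1 gives total participation of about 109 days for one Part and 183 for both.
- One Part: 35 (screening) + 8 + 28 (interval) + 8 + 30 (follow-up) = 109.
- Both Parts: 109 + 8 + 28 + 8 + 30 = 183.

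Both agree, so 8-day maximum periods and a 30-day follow-up are the right blocks. Protocol 5.1 gives the range of a confinement: "for approximately 6 to 8 days, depending on each subject's gastrointestinal motility".

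**Window lengths under SAP 9.2.3.1**

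| Subject | Period 1 | Period 2 |
|---|---|---|
| Starts open-label Creon at discharge from both periods | 6-8 days | 6-8 days |
| No open-label Creon after Visit 5 | 6-8 days | 6+30 to 8+30 = 36-38 days |

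The second row has a ratio of 38/8 = 4.75 to 36/6 = 6.0. If open-label Creon starts the next day and that date is counted, 6-8 becomes 7-9. Under Protocol 8.1.3 every cell is 6-8 days.

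**Effect on regimen percentages.** Inputs:
- 26 randomized in Part 1 (Protocol 8.2.2).
- 10 enrolled at Amendment 6 (SAP 2.4), or 10/26 = 38%, used to illustrate the size of the affected subset.
- 7-day periods, equal products, and a constant AE rate r per day. The rate is an assumption; the documents give none.

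P(at least one TEAE) = 1 − exp(−r × days). If a of the 10 receive the test product in Period 2 and b receive Creon, the spurious difference is (a − b) × (P37 − P7)/26.

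| r per day | P7 | P37 | Difference for a 7:3 split |
|---|---|---|---|
| 0.01 | 7% | 31% | 3.7 points |
| 0.02 | 13% | 52% | 6.0 points |
| 0.03 | 19% | 67% | 7.4 points |

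At 0.02 the regimen percentages are (19 × 0.1306 + 7 × 0.5229)/26 = 23.6% and (23 × 0.1306 + 3 × 0.5229)/26 = 17.6%. In window-days for the 10 subjects, a 5:5 split gives 220 against 220. A 7:3 split gives 7×37 + 3×7 = 280 against 3×37 + 7×7 = 160.

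Under independent 1:1 allocation, a split of 7:3 or more uneven in either direction has probability 2 × (120+45+10+1)/1024 = 0.34. The expected difference is zero.

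**The gap between the summaries.** Take a Part 1 subject enrolled before Amendment 6 who took open-label Creon after Visit 5. SAP 9.2.3.1 closes the TEAE window at that dose. The third bullet of SAP 9.2.2 stops at the first Period 2 dose, and the last bullet excludes the subject by enrolment date. Later AEs fall in neither summary. The cut-off is also worded two ways within 9.2.2: the first bullet covers enrolment under Amendment 6 or later, and the last covers enrolment after it. Subjects enrolled under Amendment 6 itself are therefore unclear.

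**The case against.** The strongest reply is that the SAP largely does what the protocol asks. Protocol 8.1.3 wants AEs during open-label Creon summarised separately, and closing the window at the first open-label dose achieves that. For anyone who starts open-label Creon at discharge, the two definitions nearly coincide. Pancrelipase is not absorbed (Protocol 5.3.2), the protocol sees no carry-over concern for study endpoints (5.6.1), and safety is descriptive. This stands, and it limits the consequence. It also favours the protocol's short window for everyone over a 30-day tail for a subset.

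A reader might infer that no event after a test product is ever tabulated against it once open-label Creon starts. That goes too far. The AE overview in SAP 9.2.3.2 has an all-deaths row not limited to treatment-emergent events, and SAP 9.2.3.4 covers SAEs and discontinuations without saying treatment-emergent, although it sits under the double-blind heading. An event on the first open-label date meets both definitions.

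A reader might also infer that the rule biases the comparison for or against the new product. It does not do so systematically: the inequality is between periods, and 1:1 sequence allocation balances it in expectation. Blocking, on which the documents are silent, would lower the 0.34.

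Nor is it established that early Part 1 subjects had no open-label Creon after Visit 5. The restricted bullet in SAP 9.2.2 suggests it, SAP 6.0 has no matching restriction, and the superseded protocol versions are not available. The long window and the unreported follow-up cannot both apply to the same subject; each is what follows under one answer to that question. Finally, 10 is the enrolment count at the amendment, not the number affected and not an upper bound.

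**Conclusion.** The point holds as a mismatch between current rules. The protocol and SAP define different TEAE windows, and the SAP's depends on open-label supply. Either answer to the unresolved question leaves a defect: without open-label Creon after Visit 5, a Part 1 subject has 36-38 days in Period 2 against about 6-8 in Period 1; with it, an earlier-enrolled subject's follow-up AEs drop out of both summaries.

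The size is modest. In the illustration, 6.0 points is about 1.6 of 26 subjects, conditional on a 7:3 split, 10 affected subjects and a constant assumed rate that is the same in confinement and at home. The primary CFA analysis and the non-inferiority conclusion are untouched. The correction should still be made, because the by-regimen TEAE percentage is the main safety comparison and the remedy uses data already collected.

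**What to change.** 1. In SAP 9.2.3.1, end the TEAE window for both periods and all subjects at the end of the double-blind period as the protocol defines it: Visit 3 or Visit 5, or early termination. This gives 6-8 days in both periods for subjects who complete them.
2. In the last bullet of SAP 9.2.2, replace the enrolment-amendment condition with a condition on intake: subjects who took open-label Creon after Visit 5.
3. Report AEs starting after Visit 5 in subjects without open-label Creon in a separate post-treatment summary or listing that shows the preceding regimen, so that none are lost.
4. If post-treatment AEs are shown by preceding regimen for all subjects, present those after Period 1 and after Period 2 separately. Follow-up before the next double-blind dose is about 1 to 28 days after Period 1 and 30 days after Period 2.

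Extending a 30-day tail to everyone would not solve the problem. The first Period 2 dose would still cut Period 1, giving 7-9 days with direct rollover or 34-36 days with a 28-day interval, against 36-38 in Period 2.

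The cost is SAP wording and one small table or listing. The downside is slightly fewer TEAEs for early Part 1 subjects, with the later events shown separately.
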